For the rat 13-week toxicology study, due to polymorphism of CYP2D1, genotyped rats (low--clearance genotype) were used to ensure exposure following oral administration. In the 13-week genotyped rat study, several animals died or sacrificed moribund at 1000 mg/kg/day following up to 3 days and 10 days of treatment in females and males (toxicokinetics group only), respectively, preceded by central nervous system (CNS) related signs including decreased locomotor activity, hypothermia, lateral/prone position, ataxic gait, or bradypnea. The highest dose was reduced to 500 mg/kg in female rats from Day 4 onward; the highest dose of 1000 mg/kg/day was maintained in male rats without further event. In the surviving animals, there were no remarkable clinical signs, although a few episodes of loose stool, decreased activity, and irregular respiration were found in a limited number of males. Low body weight without significant changes in food consumption and slight decreases in red blood cell (RBC) parameters were also observed in males. In histopathology, noteworthy test article-related changes were observed in the stomach in both sexes including hyperplasia/basophilia of neck cells and increased enterochromaffin-like (ECL) cells which was considered to be correlated with an increase in serum gastrin.

In the lower dose groups (30 and 100 mg/kg/day) there were no test article-related changes with exception of salivation likely secondary to the palatability of dosing formulation in a limited number of animals at 100 mg/kg.

Nonclinical findings of note in the 13-week cynomolgus monkey study included vomiting that was observed at 100 mg/kg/day and above in several animals on multiple occasions. A few episodes of drowsiness were also noted in 2 females treated at 500 mg/kg. At 30 mg/kg, there were no test article-related changes.

In the 13-week toxicology studies, the NOAEL was 100 and 30 mg/kg in rats and monkeys, respectively.

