### 5.6.3 Laboratory Values

Laboratory results will be summarized using Système International (SI) units, as appropriate. For all quantitative parameters listed in protocol Section 9.5.1.5 Safety Assessments (Laboratory Measurements), the actual value and the change from baseline to each post-baseline visit and to the end of treatment (defined as the last on-treatment value) will be summarized by visit, treatment group, overall and by stratification factors, using descriptive statistics. Qualitative parameters listed in protocol Section 9.5.1.5 will be summarized using frequencies (number and percentage of subjects), and changes from baseline to each post-baseline visit and to end of treatment will be reported using shift tables. Percentages will be based on the number of subjects with both non-missing baseline and relevant post-baseline results.

Laboratory test results will be assigned a low/normal/high (LNH) classification according to whether the value was below (L), within (N), or above (H) the laboratory parameter's reference range. Within treatment comparisons for each laboratory parameter will be based on 3-by-3 shift table that compares the baseline LNH classification to the LNH classification at each post-baseline visit and at the end of treatment. Similar shift tables will be used to compare the baseline LNH classification to the LNH classification for the highest and lowest value during the treatment period.

The Sponsor's Grading for Laboratory Values (see Appendix 13.1) presents the criteria that will be used to identify subjects with treatment-emergent markedly abnormal laboratory values (TEMAV). Except for phosphate, a laboratory value was determined to be a treatment-emergent markedly abnormal value (TEMAV) if the post-baseline grade increased from baseline and the post-baseline grade was greater than or equal to 2. For phosphate, a laboratory value was determined to be a treatment-emergent markedly abnormal value (TEMAV) if the post-baseline grade increased from baseline and the post-baseline grade was greater than or equal to 3. When displaying the incidence of TEMAVs, each subject will be counted once in the laboratory parameter high and in the laboratory parameter low categories, as applicable.

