#### 5.6.4 Vital Signs

Descriptive statistics for vital signs parameters (diastolic and systolic blood pressure, pulse, respiration rate, temperature and weight) and changes from baseline for above parameters as well as orthostatic changes for diastolic and systolic blood pressure, pulse will be presented by visit and treatment group, overall and by stratification factors.

Orthostatic hypotension is defined based on the following criteria per protocol:

Drop in standing systolic blood pressure  $\geq 20$  mmHg compared to supine, or drop in standing diastolic blood pressure  $\geq 10$  mmHg compared to supine.

Treatment-emergent orthostatic hypotension means if at baseline subject did not have SBP drop  $\geq 20$  and no DBP drop  $\geq 10$  compared to supine, but developed one or more of these two events during postbaseline visits.

Orthostatic tachycardia by numerical criteria is defined by the following numerical criteria:

Standing HR increases by  $>30$  beats/min compared to supine AND absolute standing HR is  $>100$  beats/min.

Orthostatic tachycardia without orthostatic hypotension will be considered a true orthostatic tachycardia and an instance of treatment emergent true orthostatic tachycardia is defined below:

1. Orthostatic tachycardia by above numerical criteria
2. No orthostatic hypotension (i.e. neither standing SBP drop by  $>20$  nor standing DBP drop  $>10$  compared to supine) at the same time point.
3. Does not meet criteria #1 and #2 at Baseline.

Additionally, instances of orthostatic hypotension by numerical criteria and treatment-emergent orthostatic hypotension, and instances of orthostatic tachycardia by numerical criteria and treatment-emergent true orthostatic tachycardia will be summarized by treatment group and visit, overall and by stratification factors.

Listing of vital signs including orthostatic changes will be provided.

In addition, the number (percentage) of subjects with clinically notable vital signs will be summarized by treatment group. Table 6 presents the clinical notable ranges.

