### 5.6.5 Electrocardiograms

12-lead ECG will be performed at the baseline and post-baseline visit. The mean QTcF and other ECG intervals based on triplicate ECG will be obtained. Descriptive statistics for ECG parameters (QTcB, QTcF, PR interval QRS duration and RR interval) and changes from baseline will be presented by visit, treatment group, overall and by stratification factors. Shift tables will present changes from baseline in ECG interpretation (categorized as normal; abnormal, not clinically significant; abnormal, clinically significant) to each post-baseline visit and to the end of treatment.

In addition, the number (percentage) of subjects with at least 1 post-baseline abnormal ECG result in QTc Fridericia during the treatment period will be summarized according to the following categories.

Clinically borderline or abnormal ECG results QTc Fridericia will be categorized as follows:

Absolute QTcF interval prolongation:

- QTcF interval >450 msec
- QTcF interval >480 msec
- QTcF interval >500 msec

Change from baseline in QTcF interval:

- QTcF interval increases from baseline >30 msec
- QTcF interval increases from baseline >60 msec

Plus at least one postbaseline QTcF interval >450 msec and increase from baseline >60 msec.

The number (percentage) of subjects, by treatment group and stratification factor, with at least 1 post-baseline abnormal ECG results during the treatment period, Weeks 2, 4, 6, 9 and 12 and EOT will be summarized according to the following categories:

- QTcF prolongation by >60 ms from baseline and absolute QTcF >450 ms
- QTcF prolongation to >500 ms
- Change from baseline of PR  $\geq$  25% to an absolute PR value of > 220 msec
- Change from baseline of QRS  $\geq$  25% to an absolute QRS value of > 120 msec.

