### 8.2.2 Treatment Duration for Safety Analyses

The treatment duration for all safety variables is considered to begin on Day 1 and ends 28 days after the last dose of study medication. Treatment emergent safety data (ie labs, vital signs and ECGs) are defined as observations that were recorded during treatment or within 28 days following the last dose of study drug, these will be flagged in the listings as “off treatment, but treatment emergent”. This data will be windowed and summarized as described below. Data after 28 days of last dose will be flagged as Post TE and listed only.

For summaries of safety by time points, the time points will be relative to date of first dose. For standardized reporting, study day windows relative to the first dose (Day 1) in the study will be applied to determine into which week the data will be mapped. All pretreatment assessments are conducted during Screening/Baseline Periods before Day 1. The Analysis Baseline is the last non-missing pretreatment assessments. Scheduled, unscheduled, and early discontinuation visits will be mapped to weeks. Table 8 below gives the mapping of relative day ranges to week for non-AE safety variables. If a subject did not have a recorded observation falling within a given range of days in order to be assigned to a week, the subject’s data for that week will be regarded as missing for summarization purposes. If there are two or more assessments in the same window, the following rules will be used:

- If the window is for the screening/baseline assessment, then the latest assessment will be used in the summary tables;
- If the window is for the follow-up assessment, then the latest assessment will be used in the summary tables;
- If the window is not for the screening/baseline or the follow-up assessment, then the assessment closest to the scheduled assessment will be used in the summary tables. Note that if two assessments are equidistant from the scheduled assessment then the last assessment of the two (within the allowable window) will be used.

Windowing Period	Study Day Range (Relative to First Dose)	Week
Screening	$(-42) \leq \text{Day} \leq (-8)$	
Baseline	$(-7) \leq \text{Day} \leq (-1)$	

Analysis Baseline	-	a
Treatment	$1 \leq \text{Day} \leq 21$	2
Treatment	$22 \leq \text{Day} \leq 35$	4
Treatment	$36 \leq \text{Day} \leq 53$	6
Treatment	$54 \leq \text{Day} \leq 74$	9
Treatment	$75 \leq \text{Day} \leq 98$	12
End of Treatment (EOT)	-	b
Follow up	Follow up visit	c

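### SAP 5.6.4 counts notable vital signs by absolute limits with no baseline condition, so the table mixes entrants already outside the limits with new cases, and its weight row measures body size rather than weight change

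*SAP*

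**What the plan says.** After the descriptive summaries and the orthostatic rules, SAP 5.6.4 adds that "the number (percentage) of subjects with clinically notable vital signs will be summarized by treatment group" and that "Table 6 presents the clinical notable ranges". SAP Table 6 gives one low and one high limit per parameter:

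- pulse <50 or >100 bpm
- temperature <36 or >38 °C
- weight <45 or >100 kg
- systolic BP <90 or >160
- diastolic BP <60 or >100

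Nothing in the sentence or the table refers to baseline. SAP 8.2.2 does not supply the link: treatment-emergent vital signs "are defined as observations that were recorded during treatment or within 28 days following the last dose of study drug", which is a time window only.

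For weight, 5.6.4 separately plans descriptive statistics by visit and treatment group "and changes from baseline for above parameters", together with a listing of vital signs. SAP 5 says that summaries of continuous variables include the minimum and maximum.

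**The concern.** A categorical safety table is there to show how many subjects in each arm developed a value of concern. This one counts anyone outside a limit, including a subject who arrived outside it and never changed. For weight the problem goes further, because 45 and 100 kg say how big a person is and nothing about whether weight moved.

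Out-of-range vital signs are a named part of the safety evaluation (Protocol 9.7.1.8, SAP 5.6). Outside the orthostatic events, SAP Table 6 is the only rule given for them. Weight also has some nonclinical background: the 13-week rat study in Protocol 7.1.1.3 reports "Low body weight without significant changes in food consumption" in males. What is at stake is the usefulness of one table, namely whether a difference between arms in new abnormal values, or in the number of subjects losing weight, could be read from it.

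**Working it through.** The documents state no figure for this table, so there is nothing to reproduce. The check compares the rules and then does the threshold arithmetic.

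**Rules side by side**

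| SAP section | Rule | Uses baseline? |
|---|---|---|
| 5.6.3, laboratory | flagged "if the post-baseline grade increased from baseline and the post-baseline grade was greater than or equal to 2" (3 for phosphate) | Yes |
| 5.6.4, orthostatic hypotension | "Treatment-emergent orthostatic hypotension means if at baseline subject did not have SBP drop" or the corresponding diastolic drop, and one then develops; the plain numerical count is shown as well | Yes, beside an absolute count |
| 5.6.4, orthostatic tachycardia | the treatment-emergent form requires absence at baseline | Yes |
| 5.6.5, PR | change of at least 25% "to an absolute PR value of > 220 msec"; QRS has the same structure | Yes |
| 5.6.5, QTcF | absolute categories are limited to post-baseline results and sit beside change categories | Through the companion categories |
| 5.6.4, SAP Table 6 | absolute limits only | No |

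**Weight thresholds** (inputs: the 45 and 100 kg limits)

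- Loss needed to be flagged low from baseline B is (B − 45)/B. For 70 kg this is 25/70 = 35.7%, and for 60 kg it is 15/60 = 25%. The loss must exceed these values, because the limit is strictly below 45 kg.
- A 70 kg subject who loses 15% reaches 70 × 0.85 = 59.5 kg and is not counted. A 44 kg subject with no change is counted.
- A fractional loss L newly crosses the low limit only if B is at least 45 and below 45/(1 − L). For L = 7%, 45/0.93 = 48.4 kg. For L = 10%, 45/0.90 = 50.0 kg.
- Loss can also remove a subject from the high range, when B is above 100 and at most 100/(1 − L). That upper bound is 107.5 kg for 7% and 111.1 kg for 10%.

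**How many entrants might already be outside a limit**

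The documents give no distribution of weight or BP. The means and SDs below are assumptions, taken as normal and scaled to the planned 91 per arm (SAP 4).

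For weight, the expected number outside at entry is 91 × [Φ((45 − m)/s) + 1 − Φ((100 − m)/s)].

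| Assumed mean/SD (kg) | Outside at entry, no change | Newly low if all 91 lost 7% | Leave the high range if all 91 lost 7% |
|---|---|---|---|
| 55/10 | 14.4 + 0.0 = 14.4 | 8.7 | 0.0 |
| 70/14 | 3.4 + 1.5 = 4.9 | 2.2 | 1.1 |
| 80/16 | 1.3 + 9.6 = 10.9 | 0.9 | 5.7 |

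In the third row, a 7% loss in every subject would lower the combined number outside the limits at Week 12.

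For systolic BP above 160 at entry, 91 × [1 − Φ((160 − m)/s)] gives 4.3 for 130/18, 9.6 for 135/20 and 14.4 for 140/20.

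**Data available**

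The schedule of assessments (Protocol Table 6) has weight at Screening and at Week 12 or early discontinuation. SAP 8.2.1 takes the last pre-dose value as baseline. A percent change therefore needs no new data.

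**The case against.** The strongest reply is that the plan does not lose weight change. SAP 5.6.4 summarizes change from baseline in weight, and with the minimum and maximum required by SAP 5 the largest loss in each arm is printed. Individual losses can be found in the listing, and a loss of concern can be reported as an adverse event and tabulated. All of this stands. A reader might infer that the plan cannot detect weight loss or shows no outliers, and the documents do not support that. A minimum shows one extreme subject per arm, however, and does not say how many subjects lost a meaningful share of weight.

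Second, pre-existing cases are balanced on average by 1:1 randomization, and exclusion criteria 17 and 21 let the investigator keep out subjects with clinically significant vital signs or poorly controlled conditions. This also stands. A reader might infer that the table would hide any drug effect. The supportable statement is that it dilutes one and adds noise. No numerical weight or BP limit bars entry, so some such subjects can be expected.

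Third, the rat finding should not be pressed. It appears in the account of the highest-dose animals. Protocol 7.1.1.3 reports no drug-related change except salivation at 30 and 100 mg/kg/day, and sets the rat NOAEL at 100 mg/kg. It makes weight worth tabulating sensibly and does not make weight loss an expected effect at 50 mg.

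Fourth, table shells and programming rules are in separate documents (SAP 9 and 11). They may show the count by visit with a baseline row, which would help. The SAP itself does not say so.

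**Conclusion.** The point holds as a minor one. As written, the SAP Table 6 count has no post-baseline or change condition and departs from the SAP's practice for laboratory, orthostatic and PR/QRS results. Its weight row cannot register a loss unless the subject crosses 45 kg, and a subject who does cross cannot be told apart from one who entered below it.

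The threshold results (about 36% from 70 kg; 45 to <48.4 kg for a 7% loss) follow from the stated limits alone. The counts of entrants outside a limit, about 5 to 14 of 91 for weight and 4 to 14 of 91 for systolic BP, rest on assumed distributions and show only the order of size.

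The consequence is noise and dilution in one descriptive safety table. There is no bias between arms, and no efficacy result, error rate or decision rule depends on it.

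**What to change.** In SAP 5.6.4 and SAP Table 6:

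1. Count a subject when a post-baseline value meets a limit and is either new (baseline inside the limit) or worse than baseline. A rule restricted to new cases would drop a subject who enters at a systolic BP of 162 and rises to 200. Because these measures are continuous, the SAP should say how much change counts as worse, as its PR/QRS rule does.
2. Keep the present absolute count beside it if wanted, labelled as including values present at entry. The orthostatic summaries already pair the two.
3. Replace or supplement the weight row with the number of subjects having a pre-specified percent decrease and, separately, percent increase from baseline. 7% is an example and is not taken from the documents. The sponsor should choose the cut-off and fix it before unblinding.

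The cost is SAP wording and one table program. No additional data or visits are needed.

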**Table 6 Clinical Notable Ranges for Vital Signs**

Vital Sign	Criterion for Low	Criterion for High
------------	-------------------	--------------------

Pulse (bpm)	< 50	> 100
Temperature (°C)	< 36	> 38
Weight (kg)	< 45	> 100
Systolic BP	< 90	> 160
Diastolic BP	< 60	> 100

### 5.6.5 Electrocardiograms

12-lead ECG will be performed at the baseline and post-baseline visit. The mean QTcF and other ECG intervals based on triplicate ECG will be obtained. Descriptive statistics for ECG parameters (QTcB, QTcF, PR interval QRS duration and RR interval) and changes from baseline will be presented by visit, treatment group, overall and by stratification factors. Shift tables will present changes from baseline in ECG interpretation (categorized as normal; abnormal, not clinically significant; abnormal, clinically significant) to each post-baseline visit and to the end of treatment.

In addition, the number (percentage) of subjects with at least 1 post-baseline abnormal ECG result in QTc Fridericia during the treatment period will be summarized according to the following categories.

Clinically borderline or abnormal ECG results QTc Fridericia will be categorized as follows:

Absolute QTcF interval prolongation:

- QTcF interval >450 msec
- QTcF interval >480 msec
- QTcF interval >500 msec

Change from baseline in QTcF interval:

- QTcF interval increases from baseline >30 msec
- QTcF interval increases from baseline >60 msec

Plus at least one postbaseline QTcF interval >450 msec and increase from baseline >60 msec.

The number (percentage) of subjects, by treatment group and stratification factor, with at least 1 post-baseline abnormal ECG results during the treatment period, Weeks 2, 4, 6, 9 and 12 and EOT will be summarized according to the following categories:

- QTcF prolongation by >60 ms from baseline and absolute QTcF >450 ms
- QTcF prolongation to >500 ms
- Change from baseline of PR  $\geq$  25% to an absolute PR value of > 220 msec
- Change from baseline of QRS  $\geq$  25% to an absolute QRS value of > 120 msec.

## 5.6.6 Other Safety Analyses

### 5.6.6.1 C-SSRS

The C-SSRS responses will be mapped to C-CASA as suggested by the C-SSRS Columbia website [http://www.cssrs.columbia.edu/clinical\\_trials.html](http://www.cssrs.columbia.edu/clinical_trials.html).

Number (percentage) of subjects with any treatment-emergent suicidal ideation, suicidal behavior, and suicidality (suicidal ideation and/or behavior) will be displayed. “Treatment-emergence” is used for any new or worsened events during randomization phase (treatment and follow-up) compared with the baseline C-SSRS assessment. This will be produced for at any point during the study, and by visit.

Shift from baseline to the maximum suicidal ideation severity rating (0=no ideation present to 5=active ideation with specific plan and intent) during randomization phase will assess worsening of suicidal ideation. Any score greater than 0 indicates the presence of suicidal ideation while a score of 4 (active suicidal ideation with some intent to act, without specific plan) or 5 (active suicidal ideation with specific plan and intent) can be used to indicate serious suicidal ideation.

### 5.6.6.2 UPDRS-III

Changes from baseline in the total score and four subscores of UPDRS-III will be summarized using descriptive statistics for continuous variable by visit and treatment group.

This scale evaluates extrapyramidal features in motor function in Parkinson’s disease. It contains 33 items in 18 categories: (1) speech, (2) facial expression, (3) rigidity, (4) finger tapping, (5) hand movements, (6) supinational and pronation movements of hands, (7) toe tapping, (8) leg agility, (9) arising from chair, (10) gait, (11) freezing of gait, (12) postural stability, (13) posture, (14) body bradykinesia, (15) postural tremor of hands, (16) kinetic tremor of hands, (17) rest tremor amplitude and (18) constancy of rest tremor. Each item is scored 0 to 4, giving a total score range 0 to 132. As far as is practical, the motor assessments should be made with the subject in the “on” state at each visit and at the same time relative to the subject’s last dose of Parkinson’s disease medication (such as L-dopa). The four subscores are for tremor, rigidity, bradykinesia and postural instability and gait difficulty (PIGD), as calculated per Section 8.4.

The above summary will be repeated where UPDRS and their subscores will be censored if there are changes in the subjects DLB motor medications, censoring will occur at the date of medication change, no imputations will be made.

## 5.7 Other Analyses

The following endpoints will be analyzed in the FAS using ANCOVA or GLMM as appropriate, with MI assuming MAR:

Change from baseline in the quality of life endpoints (total score and domain scores of DEMQOL and DEMQOL-Proxy, the EQ-5D and EQ-5D Proxy index scores, and EQ VAS scale) at 12 weeks of treatment

Percent change from baseline in CSF cGMP concentrations after 9 weeks of treatment.

The ANCOVA model will include corresponding baseline as a covariate, with treatment group and randomization stratification variables as factors.

